Primary Study Objective:	To assess the potential efficacy of iron therapy for decreasing erythrocyte protoporphyrin levels in patients with EPP and XLP
Secondary Study Objective(s):	
 1) To assess whether oral iron therapy can improve iron status and decrease plasma porphyrin levels and clinical symptoms 2) To assess if there is an improvement in the quality of life in treated patients
Study Population and Main Eligibility/ Exclusion Criteria:	
Inclusion criteria:
 
 1. Enrollment in the Longitudinal Study of the Porphyrias (7201) 2. Male or female age ≥ 18 years 3. Willing to sign informed consent form and follow protocol 4. History of nonblistering cutaneous photosensitivity 5. Biochemical findings- A marked increase in erythrocyte protoporphyrin (total erythrocyte protoporphyrin >400 ug/dL) with a predominance of metal-free protoporphyrin 6. Serum ferritin ≤ 30 ng/mL at baseline 7. Able to tolerate oral iron 
Exclusion criteria:
 
 1. History of liver or bone marrow transplant or clinically significant liver dysfunction as determined by the investigator 2. Patient reported known or suspected allergy to oral iron 3. Clinical evidence of active and ongoing GI bleeding 4. Use of any other clinical or experimental therapy in the past 3 months which could confound study results 5. Individuals with elevations of porphyrins in plasma or erythrocytes due to other diseases (i.e., secondary porphyrinemia) such as liver and

	
bone marrow diseases
 
6. Pregnancy
 
7. Patients with any clinically significant comorbid condition, which in the opinion of the investigator, precludes participation

Treatment	
Agent-	Ferrous sulfate USP
Dosage, schedule, route of administration-	325 mg capsule oral administered twice daily (total 650 mg daily) for 12 months
Safety Issues-	Gastrointestinal irritation, constipation, diarrhea, nausea, vomiting
Primary Outcome Measures:	The primary outcome is the relative difference in erythrocyte protoporphyrin levels between baseline and 12 months after treatment
Secondary Outcome Measures:	
 1) Erythrocyte protoporphyrin over time: Mean values and standard deviations will be computed at each time point and values will be compared descriptively. Additionally, a random effects longitudinal model of erythrocyte protoporphyrin with time as the predictor variable will be fit and used to assess whether subjects' erythrocyte protoporphyrin varied with time. 2) EPP-specific QOL: Mean scores and standard deviations will be computed at each time point and values will be compared descriptively 3) Safety: Rates of Adverse events will be computed and safety variables such as physical and other laboratory findings will be analyzed descriptively.
Statistical Considerations (sample size and analysis plan):	
A Bayesian approach based on the posterior distribution that the mean relative difference between baseline and 12-month erythrocyte protoporphyrin levels is greater than 0 will be used to assess the strength of potential efficacy. The posterior probability that the relative difference is greater than 0 will be computed. A probability $\geq 80\%$ (corresponding to an approximate quadrupling of the odds that iron is effective in lowering erythrocyte protoporphyrin) will be considered evidence that additional study of iron is warranted.
 
Assuming the distribution of baseline erythrocyte protoporphyrin is gamma (2.3, 861) and that baseline and 1 year values are correlated with $r = 0.7$, simulations indicate that a total sample size of 20 patients will allow us to detect an approximate quadrupling of the odds that iron is effective in lowering erythrocyte protoporphyrin if the true effect size is 10%.

Sponsors (federal, state, foundation and industry support):	National Institutes of Health (NIH)

1.1 Overview

Erythropoietic Protoporphyria (EPP) and X-Linked Protoporphyria (XLP) are inborn errors of heme biosynthesis, presenting clinically with severe, acute photosensitivity. Although the clinical presentation is similar, EPP results from autosomal recessive “loss-of-function” mutations in the ferrochelatase (*FECH*) gene, whereas XLP results from “gain-of-function” mutations in the erythroid-specific 5-aminolevulinate synthase (*ALAS2*) gene (1, 2). Mutations in the *FECH* gene reduce ferrochelatase activity to ~10-30% of normal (3). This enzymatic deficiency leads to the accumulation of predominantly metal-free protoporphyrin in erythroid and hepatic cells. In XLP, gain of function mutations result in increased enzymatic activity of erythroid-specific 5-aminolevulinate synthase 2, leading to accumulation of approximately equal amounts of metal-free and zinc-protoporphyrins (2). EPP is the most common porphyria in children and the second most common porphyria in adults. Patients with EPP and XLP present with painful cutaneous photosensitivity, generally in early childhood, presenting immediately or soon after exposure to sunlight. This pain can be accompanied by some redness and swelling of the sun exposed skin. The pain is severe and not responsive to analgesics (1). Currently there is no FDA approved treatment for EPP or XLP.

In the medical literature there are conflicting case reports on the effect of iron supplementation on EPP symptoms (4, 5, 6). In the case of an inherited deficiency of *FECH* activity, the lack of iron, a cosubstrate of *FECH*, could theoretically limit its capacity and thereby enhance the accumulation of protoporphyrin IX and in turn, aggravate the phototoxic symptoms. Iron supplementation in the case of iron deficiency is therefore hypothesized to improve EPP symptoms.

Therefore, the purpose of this study is to determine the effect of oral iron therapy for EPP and XLP patients.

The Office of Rare Diseases (ORD) of the National Institutes of Health (NIH) established a Rare Diseases Clinical Research Network (RDCRN) in collaboration with other NIH Institutes and has funded several rare diseases clinical research consortia and one Data Management and Coordinating Center. The Porphyrias Consortium was created as part of the RDCRN, to study the human porphyrias. The Porphyrias Consortium is a consortium of the academic institutions listed in the participating institutions table. All Centers in the Porphyrias Consortium are participating in this study. Additional centers may be added if funding is available.

2. Specific Aims (Hypothesis and Objectives)

The overall objectives of this study are to determine the efficacy and safety of oral iron administration in the protoporphyrrias. Efficacy will be based on erythrocyte protoporphyrin levels, photosensitivity, other clinical symptoms, and quality of life in patients with EPP and XLP who have diminished iron stores (serum ferritin ≤ 30 ng/ml).

Primary Objective: To determine if oral iron therapy can decrease erythrocyte protoporphyrin levels in patients with EPP and XLP.

Secondary Objectives:

- 1) To assess whether oral iron therapy can improve iron status and decrease plasma porphyrin levels and clinical symptoms
- 2) To assess if there is an improvement in the quality of life in treated patients

This is an open label pilot study of the safety and efficacy of oral iron therapy in patients with EPP and XLP with diminished iron stores as defined by serum ferritin level.

3. Background

Erythropoietic Protoporphyrinia (EPP) is characterized by painful, non-blistering, cutaneous photosensitivity, with onset in early childhood. EPP is the most common porphyria in children and the third most common in adults (after porphyria cutanea tarda and acute intermittent porphyria). Reports of prevalence vary between 5 and 15 cases per million population. (2-4)

EPP is most often due to decreased activity of ferrochelatase (*FECH*), the enzyme that catalyzes the incorporation of ferrous iron into PPIX, the final step in the production of heme. The pattern of inheritance is autosomal recessive. Homozygosity for a *FECH* mutation is rare. In most cases, the decreased activity is a consequence of a combination of an inherited inactivating mutation affecting one *FECH* allele and an intronic polymorphism that is common in the population and which alters splicing of the other allele. The alternative splice site, when used, produces a non-functional *FECH* mRNA. The alternative splice site is used approximately 40% of the time. Therefore, the polymorphic allele produces approximately 60% of normal *FECH* activity, and for this reason, is termed hypomorphic. When the hypomorphic *FECH* allele is in *trans* with the non-functional mutant allele, the result is 30% or less of the normal *FECH* enzyme activity. This subnormal *FECH* activity becomes rate-limiting, resulting in accumulation of intracellular protoporphyrin IX (PPIX). Although the defect is presumably expressed in all tissues, the PPIX responsible for photosensitivity derives primarily from marrow reticulocytes. X-linked Protoporphyrinia is less common than EPP, occurring in ~10% of cases, but has the same phenotype, and results from gain of function mutations in the *ALAS2* gene, leading to the overproduction of protoporphyrin in the bone marrow (2, 4).

Significance

There are no FDA-approved treatments for EPP and XLP other than pharmaceutical grade β carotene (Lumitene), which was FDA approved for EPP and later classified as a nutritional product and is now available without a prescription. Cysteine and Vitamin C have been studied in these patients, but with little convincing evidence of efficacy. Most patients report minimal, if any improvement with any of these products (7). There have been few multicenter trials, which are required for collecting high quality data, on safety and efficacy of new and existing treatments. Afamelanotide (α -melanocyte stimulating hormone), one of the few drugs under investigation for the treatment of EPP and XLP

completed Phase 3 trials in August 2013. Although beneficial, afamelanotide acts by darkening the skin rather than by decreasing circulating protoporphyrin levels (5, 8). No treatments reported to date, other than marrow transplantation and Panhematin® infusions, given in the setting of acute liver failure, decreases erythrocyte protoporphyrin levels, in these patients. A large proportion of patients with the EPP phenotype are mildly iron deficient, but that proportion is not well defined, and its significance and influence on disease severity is not known. We believe that iron therapy in patients with the EPP phenotype and low iron stores has the potential to increase iron availability and thereby increase protoporphyrin utilization for heme synthesis. Additionally, we also believe, that this therapy, may sufficiently decrease protoporphyrin accumulation to be clinically beneficial. If so, this would provide significant and low cost benefit to these patients.

Erythropoietic Protoporphyrin and Iron: As noted above, EPP is caused by deficiency in ferrochelatase, the last enzyme in the heme biosynthetic pathway. The role of ferrochelatase is to catalyze the insertion of ferrous iron into protoporphyrin to form heme (1). Defective ferrochelatase activity results in the accumulation of protoporphyrin initially in the marrow and then in erythrocytes and plasma, which circulate to the skin, liver and other tissues leading to the clinical symptoms. Recent reports suggest that the availability of iron modulates ferrochelatase activity by regulating the amount of correctly spliced *FECH* mRNA (9), and thus iron appears to play an important role in disease expression.

Many patients with EPP, also have mild anemia, with evidence of iron deficiency, including microcytosis and low serum ferritin and iron levels (10). In a Swedish cohort, of EPP patients, about 45% had low ferritin levels (11). In our longitudinal study, 52% of EPP and XLP patients had low ferritin at baseline. Other than microcytosis, there is little evidence of impaired erythropoiesis or abnormal iron metabolism in these patients. Although inappropriately low iron absorption has been proposed to explain these findings, this has not been substantiated.

The role of iron replacement in EPP and the clinical response to increased iron is controversial, some reports suggest clinical improvement (12, 13, 14, 15) while others describe an exacerbation of photosensitivity (16, 17). Notably, an increase in protoporphyrin levels, has never been documented, in EPP patients treated with iron. Based on these conflicting reports, clinical practice varies among physicians with some using oral iron replacement in EPP patients with low iron stores and others choosing no intervention. No results or follow up on the effectiveness of oral iron therapy have been reported. A recent report from the U.K. showed clinical and biochemical improvement in a single EPP patient that had been treated with low doses of intravenous iron (17). Hemin therapy has also been used in EPP patients with advanced liver disease prior to transplantation and decreases in erythrocyte and plasma protoporphyrin levels have been observed (18). Although the mechanism of action is unclear, a possible hypothesis is that hemin, which contains iron, improves iron stores in these patients by providing iron, as well as bypassing the deficient *FECH* enzyme, leading to a decrease in protoporphyrin levels. Results from previous studies of the natural history of EPP/XLP

suggest that there is little change in erythrocyte protoporphyrin levels over time and there is little intra-individual variation (11).

Interestingly, oral iron replacement in one patient with XLP with diminished iron stores also led to a decrease in erythrocyte protoporphyrin levels (2). We also administered oral iron to a patient with XLP and observed a 20% decrease in erythrocyte protoporphyrin levels. We have now enrolled a large number of patients in an EPP Natural History study, several of whom were treated in the past with oral or intravenous iron therapy and experienced improvements in iron status without adverse consequences before they entered our studies. Unfortunately, serial measurements of protoporphyrin levels were not done prior to enrollment in our longitudinal studies. While these reports and our experience to date suggest that iron replacement can improve iron status and may decrease erythrocyte protoporphyrin levels, the efficacy and safety of iron therapy in EPP and XLP have not been systematically investigated, and whether or not to use iron in these patients remains an unanswered clinical question.

A recent pilot study (19) showed that patients with EPP and XLP absorb oral iron with post dose increases in serum iron. In addition, the serum and urine hepcidin were not inappropriately increased in these subjects at baseline and did not increase over time after oral ferrous sulfate. Thus, the basis of iron deficiency in EPP/XLP patients and the effectiveness and safety of iron therapy are not clear and warrant further investigation.

This provides the rationale for a pilot therapeutic study with oral iron in EPP and XLP patients with well characterized phenotypes, genotypes, and iron status, with serial measurements of protoporphyrin levels in erythrocytes and plasma during treatment.

Preliminary data:

Laboratory Studies: To examine the additive effect of iron on ferrochelatase (*FECH*) activity, an in vitro assay was set up using lymphoblastoid cell lines. Blood samples were collected from the EPP patients, who carried the p.C411G mutation (no detectable enzymatic activity (20) in trans to IVS3-48C (genotype M/C) and from healthy donors (genotype T/T). Lymphoblastoid cell lines were established from these samples by transformation of the peripheral B lymphocytes with Epstein-Barr virus following a standard procedure (21). After treatment of cells with ammonium iron (III) citrate for 24 hours, *FECH* activity was determined by fluorometric measurement of zinc-deuteroporphyrin formation (nmol zinc-deuteroporphyrin/hour/mg protein at 37°C) (22) and compared to the value of lymphoblastoid (T/T) without any treatment. When lymphoblastoid cells (M/C) were treated with iron (III), *FECH* activity increased and reached 35.5%, up to 100 μ M, followed by a decrease at increased iron concentrations (Figure 1). Dissimilarly, treatment of lymphoblastoid cells (T/T) with iron (III) below 100 μ M only resulted in a slight decrease in *FECH* activity. These results suggest that

treatment of iron (III) at proper concentrations (below 100 μ M) may help to increase the *FECH* activity in cells with loss-of-function mutations on *FECH* gene.

[figure not shown]

Figure 1. Effect of Iron (III) on the ferrochelatase activity of lymphoblastoid cell lines established from healthy donors (IVS3-48T/T) and patients (C411G/IVS3-48T>C). Data are expressed as mean \pm standard deviation of four experiments.

4.1 Inclusion Criteria

1. Enrollment in the Longitudinal Study of the Porphyrias (7201)
2. Male or female age ≥ 18 years
3. Willing to sign informed consent form and follow protocol
4. History of nonblistering cutaneous photosensitivity
5. Biochemical findings - A marked increase in erythrocyte protoporphyrin (total erythrocyte protoporphyrin >400 ug/dL) with a predominance of metal-free protoporphyrin
6. Serum ferritin ≤ 30 ng/mL at baseline
7. Able to tolerate oral iron

4.2 Exclusion Criteria

1. History of liver or bone marrow transplant or clinically significant liver dysfunction as determined by the investigator
2. Known or suspected allergy to oral iron based on patient report
3. Clinical evidence of active and ongoing GI bleeding
4. Use of any other clinical or experimental therapy in the past 3 months
5. Individuals with elevations of porphyrins in plasma or erythrocytes due to other diseases (i.e. secondary porphyrinemia) such as liver and bone marrow diseases
6. Pregnancy
7. Patients with any clinically significant comorbid conditions, which in the opinion of the investigator, precludes participation

4.3 Recruitment of Participants

The methods of recruitment will be:

- A. Patients followed by any of the Investigators in the Porphyrias Consortium. Each of the Investigators is a Porphyria specialist in a Porphyria Center, and provides clinical care to individuals suspected of and diagnosed with porphyria, providing diagnostic and follow-up evaluations, consultations, and/or treatment. For such patients who are likely to be eligible for the study, the Investigators will either discuss the study with the patient during a clinical visit or will contact the patient by telephone, email, or mail, as appropriate per site-specific IRB approval. Any efforts to contact and recruit patients and families will be with IRB approval and adhere to standards for ethical conduct of research and be fully HIPAA compliant.
- B. Referrals from the American Porphyria Foundation (APF) to the Porphyrias Consortium centers. The APF is an advocacy group that provides education about porphyria to patients, their families, healthcare professionals, and the public and supports porphyria research. Their outreach program includes a website, as well as periodic newsletters and special announcements emailed and/or mailed to individuals who have registered with the APF with information about new developments in treatment, porphyria-related education opportunities, and research studies available through the Porphyria Consortium. Information about research studies includes contact information for the studies if they are interested in obtaining additional information or participating.
- C. Patients contacted through the Rare Diseases Clinical Research Network (RDCRN) Contact Registry. Individuals can register on-line or by faxing or mailing the registration form expressing an interest in receiving information about research studies for which they might qualify. The Contact Registry is managed by the Data Management Coordinating Center (DMCC) of the RDCRN. The DMCC can refer them directly to the Porphyria Consortium for contact by their closest clinical site. The DMCC sends information by email

about research studies along with contact information permitting registrants to obtain additional information about participating.

- D. Non-study Physician referrals. Physicians providing clinical care to individuals suspected of or diagnosed with EPP who are not investigators in this study may refer patients who may be eligible for and express interest in the study to a Porphyrias Consortium center.
- E. Self-referrals, including family members of individuals diagnosed with EPP (proband) and other individuals who may have heard about the study from other subjects or prospective subjects. In the case of family members, initial contact with the family member will not be made by the study team. The proband will be asked to contact such family members, requesting that they contact the study coordinator or to register through the RDCRN-Porphyria Consortium if interested in obtaining additional information or participating.

In the case of patients followed by one of the Consortium Investigators, the physician/Investigator or study coordinator will either: (a) contact the patient by telephone, email or mail informing him/her of the study and requesting that he/she contact the study coordinator if interested in obtaining additional information or participating, or; (b) discuss the study in-person during a clinical visit; informed consent may be obtained at this time. In all other cases, prospective subjects are instructed to contact the study coordinator, either the Project Manager or a site-specific study coordinator, by telephone, email or mail if interested in obtaining additional information or participating.

4.4 Retention Strategies

EPP and XLP are rare diseases. Only a small number of specialists have the expertise to evaluate and treat affected individuals. Clinical relationships established by the investigators with patients who enroll in this pilot study will provide a context for increased communication with patients and their primary physicians that can facilitate retention. Furthermore, this study will provide a number of beneficial services to the participants and their primary physicians that will enhance retention. These include periodic evaluations, repeat laboratory testing, and information on new research developments in the field. Coordinators and other personnel at each site will also work to maintain close contact with participants, including regular clinic visits, newsletters and communication by phone, email and web sites. Counseling services will be provided so that patients and families are made aware of the results of studies and their correct interpretation. There will be no charge for the physician services or laboratory tests done as part of this pilot study.

4.5 Data Elements

The following laboratory tests and procedures will be used as the primary data elements:

- Erythrocyte protoporphyrin
- Plasma total porphyrins
- A complete blood count with differential
- Iron studies (serum iron, TIBC, Transferrin saturation)

- Serum ferritin
- Hepatic function panel (serum ALT, AST, alkaline phosphatase, total and direct bilirubin, albumin, total protein)
- EPP-specific Quality of Life Questionnaire

These will be completed at each study visit, and an adverse event review will be completed bi-weekly.

4.6 Study Procedures

Baseline/Screening Visit:

- Patients will be admitted to the Clinical Research Unit or a comparable facility for ~2 hours. All patients will be enrolled in the Longitudinal Study and the diagnosis of EPP or XLP and inclusion/exclusion criteria will be reviewed prior to baseline visit.
- A complete history and physical exam will be performed
- All concomitant medications will be recorded- if the subject is currently taking an iron supplement they will be instructed to discontinue it for at least 4 weeks and return for re-screening.
- Subjects taking Lumitene at screening will be asked to discontinue it for at least 4 weeks and return for re-screening.
- Patients will be asked to complete an EPP-specific quality of life questionnaire
- Laboratory studies will include:
 - A complete blood count with differential
 - Serum iron
 - TIBC
 - Serum ferritin
 - Transferrin saturation
 - Hepatic function panel
 - Erythrocyte protoporphyrin levels with metal-free and zinc ratio
 - Plasma total porphyrins
- Two yellow top ACD tubes will be collected and banked for future RNA and protein studies in this patient population
- Subjects will be instructed to take ferrous sulfate 325 mg BID with water starting the next day on an empty stomach following discharge.
Subjects will be discharged with a 3 month supply of medication with some surplus to account for dropped pills.

The first dose of oral ferrous sulfate (two 325 mg tablets) will be administered within 30 days of the screening visit.

For patients with a borderline ferritin level, re-screening will be allowed within 60 days of the original screening date. Only ferritin and erythrocyte protoporphyrin levels should be done at the re-screening visit. If the ferritin level is ≤ 30 ng/mL on re-screening, the first dose of oral ferrous sulfate will be administered within 30 days of the re-screening visit.

Follow Up Phone Calls:

- Coordinators will call the subject once a month (+/- 7 days) to review adverse events and concomitant medications.

3 Month, 6 Month, and 9 Month Study Visits (+/- 7 days):

- A review of systems will be performed, a physical exam will only be performed at the 6 Month visit
- Adverse events will be reviewed
- All concomitant medication changes will be recorded
- Patients will be asked to complete an EPP-specific quality of life questionnaire
- Laboratory studies will include:
 - A complete blood count with differential
 - Serum iron
 - TIBC
 - Serum ferritin
 - Transferrin saturation
 - Hepatic function panel
 - Erythrocyte protoporphyrin levels with metal-free and zinc ratio
 - Plasma total porphyrins
- Two yellow top 10mL ACD tubes will be collected and banked for future RNA and protein studies in this patient population (at 6 month visit only)
- Pill counts will be performed and recorded to monitor compliance
- Old medication bottles will be collected
- Subjects will be discharged with a 3 month supply of medication with some surplus to account for dropped pills.

12 Month Study Visit (Or Early Termination Visit) (+/- 7 days):

- Patients will be admitted to the Clinical Research Unit or a comparable facility for ~2 hours
- A review of systems and physical exam will be performed
- Adverse events will be reviewed
- All concomitant medication changes will be recorded
- Patients will be asked to complete an EPP-specific quality of life questionnaire
- Laboratory studies will include:
 - A complete blood count
 - Serum iron
 - TIBC
 - Serum ferritin
 - Transferrin saturation
 - Hepatic function panel
 - Erythrocyte protoporphyrin levels with metal-free and zinc ratio
 - Plasma total porphyrins
- Two yellow top 10mL ACD tubes will be collected and banked for future RNA and protein studies in this patient population

- A single dose of oral ferrous sulfate (two 325 mg tablets) will be administered with water
- Old medication bottles will be collected and pills will be counted for compliance

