4.7 Schedule of Events

	Screening	Day 0	1 Month 2 Month (via telephone)	3 Month	4 Month 5 Month (via telephone)	6 Month	7 Month 8 Month (via telephone)	9 Month	10 Month 11 Month (via telephone)	12 Month
	(Day -30 to -1)		(± 7 Days)	(± 7 Days)	(± 7 Days)	(± 7 Days)	(± 7 Days)	(± 7 Days)	(± 7 Days)	(± 7 Days)
Informed Consent	X									
Inclusion/Exclusion Criteria Review	X									
Labs (CBC, Iron, TIBC, Ferritin, Transferrin Sat, HFP)	X			X		X		X		X
Erythrocyte protoporphyrin levels & plasma porphyrins	X			X		X		X		X
2 Yellow top ACD tubes for banked samples	X					X				X
Urine/serum Pregnancy	X					X				X
Medical History review	X									
Review of Systems	X					X				X
Physical Exam	X					X				X
Vital Signs	X			X		X		X		X
EPP QoL Questionnaire	X			X		X		X		X
Provide 3 Month Supply of Medication		X*		X		X		X		
Pill Count				X		X		X		X
Con Med Review	X			X		X		X		X
AE Review			X	X	X	X	X	X	X	X
Review Compliance			X		X		X		X	

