5.9 Quality Control: Study Related Procedures

The standard laboratory measures (CBC, CMP, Iron panel, etc) will be performed at each sites' central laboratory. Erythrocyte protoporphyrin measurements will be performed in the CLIA certified laboratory of [name], University of Texas Medical Branch, Galveston, TX.

The investigational pharmacy at each site will be responsible for drug accountability while the investigators/coordinators will be responsible for compliance of the subjects. The Investigational Drug Service at the Icahn School of Medicine at Mount Sinai will serve as the coordinating pharmacy for this study.

6. Statistical Considerations

The primary outcome is the relative difference in erythrocyte protoporphyrin levels between baseline and 12 months after treatment. A Bayesian approach based on the posterior distribution that the mean relative difference between baseline and 12-month erythrocyte protoporphyrin levels is greater than 0 will be used to assess the strength of potential efficacy of oral iron therapy.

The procedure will be carried out as follows. Let X_0 and X_{12} be the observed mean erythrocyte protoporphyrin level at baseline and 12 months. Let X_0 and X_{12} be correlated with a Pearson correlation coefficient of r and let $d = \frac{X_0 - X_{12}}{X_0}$ and $\Theta = \frac{\mu_0 - \mu_{12}}{\mu_0}$.

Based on data observed in previous studies, we assume that the distribution of

erythrocyte protoporphyrin follows a gamma distribution (see background data section below). For an individual i , $X_{0i} \sim \text{gamma}(\alpha_0, \beta_0)$ and $X_{12i} \sim \text{gamma}(\alpha_{12}, \beta_{12})$.

$X_0 = \frac{\sum_{i=1}^n (X_{0i})}{n}$, therefore $\frac{1}{n} X_0 \sim n * \text{gamma}(\alpha_0, \beta_0) = \text{gamma}(n\alpha_0, \beta_0)$ and likewise $\frac{1}{n} X_{12} \sim \text{gamma}(n\alpha_{12}, \beta_{12})$.

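### Sections 4.6 and 4.7 disagree on when study iron is dispensed and first taken relative to screening, and one version leaves no step for checking the baseline eligibility results

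*Combined protocol and SAP*

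**What the plan says.** Four pieces of text bear on when iron starts.

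- **Section 4.6, Baseline/Screening Visit bullets.** The visit includes the blood draw for ferritin and erythrocyte protoporphyrin. The list ends with "Subjects will be instructed to take ferrous sulfate 325 mg BID with water starting the next day on an empty stomach following discharge" and "Subjects will be discharged with a 3 month supply of medication with some surplus to account for dropped pills".
- **Section 4.6, sentence directly below the bullets.** "The first dose of oral ferrous sulfate (two 325 mg tablets) will be administered within 30 days of the screening visit".
- **Section 4.6, re-screening paragraph.** A patient with borderline ferritin may be re-screened up to 60 days after the original screening, with ferritin and protoporphyrin repeated. If the repeat ferritin meets the limit, the first dose follows within 30 days of re-screening.
- **Section 4.7, Schedule of Events.** Laboratory tests and the criteria review sit in the Screening column (Day -30 to -1). The first mark in the row "Provide 3 Month Supply of Medication" is in a separate Day 0 column. It carries an asterisk whose footnote is not in the text available to this review.

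The eligibility rules concerned are in section 4.1: "Serum ferritin ≤ 30 ng/mL at baseline" and "total erythrocyte protoporphyrin >400 ug/dL". Section 4.6 also states that "inclusion/exclusion criteria will be reviewed prior to baseline visit". Section 7.1 has the site attest eligibility at registration but does not place that step before or after dispensing.

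**The concern.** The bullets put the qualifying blood draw, the hand-over of drug and the instruction to start the following day into one visit. Nothing in that list tells the site to look at the ferritin and protoporphyrin results first. The other three texts describe a gap between screening and first dose, and one of them makes the dose conditional on a result.

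Two things are at stake if a site follows the bullets.

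- **Eligibility.** A patient could be on iron when the baseline ferritin or protoporphyrin turns out to miss the criterion. Section 5.7 applies an intent-to-treat approach and keeps data acquired before termination in the primary analysis. In a trial of 20, each such patient is 1/20 = 5% of the sample. Section 5.3 also warns that iron may raise protoporphyrin and worsen symptoms, so exposing someone not shown to be eligible is a safety matter too.
- **Re-screening.** A borderline patient could have ferritin and protoporphyrin repeated while taking study iron. Section 4.6 itself treats iron as a reason to defer screening: a patient taking an iron supplement must stop for at least 4 weeks before re-screening.

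**Working it through.** No power or sample-size figure is involved. The check compares the texts and counts days on the visit windows.

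**Inputs.** Screening day s runs from -30 to -1 (section 4.7). The bullet starts iron on day s + 1 (section 4.6). First supply is at Day 0 (section 4.7). The re-screening window is 60 days, and the first dose comes within 30 days after it (section 4.6).

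**Step 1: timing of the first dose.** With s between -30 and -1, s + 1 lies between Day -29 and Day 0. It equals Day 0 only when s = -1. That is 1 of the 30 permitted screening days; on the other 29, iron would start before the schedule's Day 0. If Day 0 is defined as the first dose, the next-day rule forces screening to Day -1 and leaves the 30-day window without purpose.

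**Step 2: timing of dispensing.** The bullets hand over the supply on day s, and s is never 0. The schedule marks no supply at Screening. The two conflict on all 30 permitted days.

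**Step 3: form of the first dose.** The bullet has the patient take 325 mg twice daily after discharge. The next sentence has two 325 mg tablets administered. These differ in who gives the first dose and in what it consists of. This review does not judge which is right.

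**Step 4: can the screening results exclude a patient?** Yes. The ferritin criterion is tied to baseline, the schedule places the criteria review at Screening, and the re-screening paragraph makes dosing conditional on ferritin. That paragraph has a purpose only if a screening ferritin can fail.

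**Step 5: are the results available by the next day?** The documents do not say. For protoporphyrin, section 5.9 states "Erythrocyte protoporphyrin measurements will be performed in the CLIA certified laboratory" and names a single laboratory for the six participating sites, so a next-day result looks doubtful for sites elsewhere; that is an inference. Section 5.9 has standard tests, including the iron panel, run at each site's own laboratory. Ferritin plausibly belongs there and could be back sooner.

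**Step 6: re-screened patients.** Under the re-screening paragraph, the first dose may come up to 60 + 30 = 90 days after the original screening, which lies outside the schedule's Day -30 unless the window restarts at re-screening. The schedule does not say that it does.

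**The case against.** The strongest defence is that the bullet is simply misplaced and the intended order is results first. The 30-day sentence, the re-screening paragraph and the Day 0 column all point that way. One coherent reading is that two tablets are administered on Day 0, as the 12-month visit also has a two-tablet dose administered, and twice-daily dosing starts the day after. The missing footnote to the Day 0 mark, and the opening of section 4, which was also unavailable, might confirm this. The defence is plausible but does not remove the conflict: the bullet still stands under the screening visit as an instruction to sites.

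It can also be said that few ineligible patients would reach the visit. Every patient is already in the Longitudinal Study, criteria are reviewed beforehand, and section 8.6 has sites identify eligible subjects before approaching them. This stands as a limit on frequency. It does not settle the baseline ferritin, which can differ from an earlier value.

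Three stronger readings are tempting and are not supported:

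- **That about half of those screened would start iron while ineligible.** Section 3 reports low ferritin in 45% of a Swedish cohort and 52% of the Longitudinal Study patients. It gives no cut-off, so neither figure is a pass rate for 30 ng/mL, and both ignore the prior review.
- **That re-screened patients would have up to two months of drug before the second baseline.** The paragraph governing them puts the first dose after re-screening. Such exposure arises only if a site acts on the bullet and overlooks that paragraph.
- **That the results cannot be known before dosing.** No turnaround time is stated.

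**Conclusion.** The contradiction holds. It is complete for dispensing (30 of 30 permitted screening days) and near-complete for the start of dosing (29 of 30, taking Day 0 as the first dose). As placed, the next-day bullet allows drug to be taken before the baseline ferritin and protoporphyrin are checked, and allows a borderline patient to be re-screened on study iron, at odds with the section's own 4-week iron washout.

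The number of patients affected cannot be estimated from the documents. A reader might infer that the primary comparison is compromised; that does not follow. For patients not re-screened, baseline protoporphyrin is drawn before dosing on any reading, and the sample-size figures are untouched. The exposure is to eligibility errors, to the baseline of any patient re-screened on drug, and to inconsistent practice across sites. The conclusion assumes that the footnote to the Day 0 mark does not already resolve the sequence; even if it explains Day 0, the bullet in section 4.6 would need correcting. The point should be fixed, but it is a problem of operative wording and not a flaw in the design.

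**What to change.** Reconcile four texts into one sequence: the next-day bullet and its dispensing line, the 30-day sentence, the re-screening paragraph, and the Day 0 column with its footnote. The sequence should define Day 0, name the visit at which drug is handed over, and say how the screening window applies to a re-screened patient. It should also state where the section 7.1 eligibility attestation, based on the screening results, falls relative to dispensing. Which sequence and which form of first dose are correct is for the sponsor and the investigators to decide.

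The cost is protocol wording and, depending on the sequence chosen, possibly a dispensing step separate from the screening visit. Sample size and analysis do not change.
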